6.5.2. Fever at OAV#1 or OAV#2

Two variables are used to define Fever at OAV#1 or OAV#2:

- ACRTEMP: Has the subject had a recorded temperature > 38.3 °C (100.9 °F) in the past 24 hours? (Yes/No)
- ACRFEV: If Yes, was fever attributed to a process unrelated to the prior diagnosis of pneumonia? (Yes/No)

Fever at Outcome Assessment Visit #1 and Fever at Outcome Assessment Visit #2 both involve several data components and have complex rules for when they are considered missing versus when fever is considered present or not present. The below logic describes the rules. Note that “fever is observed as a solicited event” only if a temperature of ≥ 38.3 °C (100.9 °F) was recorded on the day of the Outcome Assessment Visit or on the day prior to the Outcome Assessment Visit and either had no recorded confirmatory measurement at least 15 minutes after the first measurement or else the confirmatory measurement also indicated a temperature of ≥ 38.3 °C (100.9 °F). Fever at the OAV is never missing if the OAV did occur (specifically, ACRTEMP not missing), and the vital signs measurement at the visit and the actual temperatures reported by parents and recorded on the solicited events form (SRS) are treated as optional and supplemental data in the determination of the presence of fever at the visit.

- If the OAV did occur
 - o If subject had a recorded temperature ≥ 38.3 °C (100.9 °F) (ACRTEMP) and fever is not indicated as unrelated to prior diagnoses of pneumonia (ACRFEV), then fever at the OAV is present

- o If subject had a recorded temperature ≥ 38.3 °C (100.9 °F) (ACRTEMP) and fever is indicated as unrelated to prior diagnoses of pneumonia (ACRFEV), then fever at the OAV is absent
- o If subject had a recorded temperature ≥ 38.3 °C (100.9 °F) (ACRTEMP) and fever is indicated as relatedness to prior diagnoses of pneumonia (ACRFEV) is missing, then fever at the OAV is missing
- o If subject had a recorded temperature < 38.3 °C (100.9 °F) (ACRTEMP), then fever at the OAV is absent

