- Oral, rectal, axillary, or tympanic temperature $\geq 38.3^{\circ}\text{C}$ (100.9°F), confirmed by repeat measurement after at least 15 minutes, in the 24 hours preceding the Outcome Assessment Visit or measured at the Outcome Assessment Visit, unless attributed to a new process that is unrelated to the prior diagnosis of pneumonia;
- Elevated respiratory rate (RR >50 breaths/minute for children <24 months of age and >40 breaths/minute for children 24-71 months of age) at the time of the Outcome Assessment Visit;
- Presence of cough grade 2 or 3 at the Outcome Assessment Visit, (defined in Table 2).

³Solicited events (Table 3) will be captured daily until Outcome Assessment Visit #2; thereafter, parents/legal guardians will report symptoms based on memory aid and medical interview by

study staff. For those with multiple solicited events, the ordinal response table will be based upon the most severe solicited event.

Table 2: Severity of Cough

Symptom	Mild (Grade 1)	Moderate (Grade 2)	Severe (Grade 3)
Cough	Occasional coughing (less than 4 times hourly)	Frequent coughing (4 or more times an hour), interferes with sleep)	Almost constant coughing (never free of cough), makes sleep nearly impossible

Table 3. Solicited Events Grading

Symptom	Mild (Grade 1)	Moderate (Grade 2)	Severe (Grade 3)
Irritability	More irritable or fussy than usual but can be consoled; no interference with smiling/playing	Irritability or fussiness that is difficult to console and interferes with smiling and playing	Irritability or fussiness that lasts for more than 4 consecutive hours in a 24 hour period or cannot be consoled
Vomiting	1 episode/day	2-3 episodes/day	≥4 episodes/day
Diarrhea	Looser than normal stools occurring 3-6 times/day	Looser than normal stools occurring >6 times/day	Bloody diarrhea, or diarrhea that requires medical intervention, laboratory testing, or hospitalization
Allergic Reaction	Localized rash or pruritus without rash	Diffuse rash (maculopapular or urticarial)	Generalized rash consistent with Stevens-Johnson Syndrome, erythema multiforme, or toxic epidermal necrolysis; anaphylaxis; or angioedema
Stomatitis	Oral lesions associated with parenteral report of mild oral discomfort	Oral lesions associated with difficulty swallowing, but able to eat and drink	Oral lesions associated with inability to swallow solids or liquids; requires medical intervention, IV fluids, or hospitalization

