- Oral, rectal, axillary, or tympanic temperature $\geq 38.3^{\circ}\text{C}$ (100.9°F), confirmed by repeat measurement after at least 15 minutes, in the 24 hours preceding the Outcome Assessment Visit, unless attributed to a new process that is unrelated to the prior diagnosis of pneumonia;

- Elevated respiratory rate (RR >50 breaths/minute for children <24 months of age and >40 breaths/minute for children 24-71 months of age) at the time of the Outcome Assessment Visit;

- Presence of cough grade 2 or 3 at the Outcome Assessment Visit, defined as Grade 0 (no cough), Grade 1 (Occasional coughing [less than 4 times hourly]), Grade 2 (frequent coughing [4 or more times an hour], interferes with sleep), Grade 3 (almost constant coughing (never free of cough), makes sleep nearly impossible);

³ Solicited events will be captured daily until Outcome Assessment Visit #2; thereafter, parents/legal guardians will report symptoms based on memory aid and medical interview by study staff. For those with multiple solicited events, the ordinal response table will be based upon the most severe solicited event.

Day 1: Day 1 begins at the time the first dose of study product is administered and ends at 11:59 PM of that same day. If a subject has no recorded receipt of study product at the time of the analysis, then Day 1 will be defined as the date 5 days after the date of initiation of the initial antibiotic.

DOOR at Outcome Assessment Visit #1: Defined as above, using DOOR components from the following Study Days.

Adequate Clinical Response: Day 1 – Day 5

Resolution of Symptoms:

- o Fever as measured in the 24 hours prior to Outcome Assessment Visit #1. If a subject has a fever according to a single measurement, but no repeat measurement after at least 15 minutes has been performed, the subject will be analyzed as having a fever. If a subject has a fever according to the measurement taken as a part of vital signs

during Outcome Assessment Visit #1, the subject will be analyzed as having a fever at Outcome Assessment Visit #1. If the vital signs measurement shows no fever, and the parental assessment of fever during the previous 24 hours is missing, then fever will be treated as missing.

- o Respiratory Rate and Cough: determined at Outcome Assessment Visit #1

Solicited Events: Day 1 – Day 5

Number of Days of Antibiotic Use: Day 1 – Day 5

DOOR at Outcome Assessment Visit #2: Defined as above, using DOOR components from the following Study Days.

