6.5.3. Resolution of Symptoms at OAV#1 or OAV#2

Resolution of symptoms is defined as the absence of all of the following:

- Fever at the OAV, as defined above
- Elevated respiratory rate (RR >50 breaths/minute for children <24 months of age and >40 breaths/minute for children 24-71 months of age) at the time of the Outcome Assessment Visit (VS1.RESPB);
- Presence of cough grade 2 or 3 at the Outcome Assessment Visit (ACRCGHSV)

If the subject died at any point of participation in the study, then the subject will be analyzed as not having resolution of symptoms at either Outcome Assessment Visit. Otherwise, if the subject did not have adequate clinical response at OAV#1 or OAV#2, then the subject will be analyzed as not having resolution of symptoms at the respective Outcome Assessment Visit(s). Otherwise, if fever, elevated respiratory rate, or presence of grade 2 or 3 cough is indicated at OAV#1 or OAV#2, then the subject does not have resolution of symptoms at the respective Outcome Assessment Visit (regardless of whether some components of the resolution of symptoms are missing). Otherwise, if fever, respiratory rate, and presence of cough are all non-missing and are indicated as 'No' at OAV#1 or OAV#2, then the subject has resolution of symptoms at the respective Outcome Assessment Visit. Otherwise, resolution of symptoms is missing at the Outcome Assessment Visit.

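### SAP 6.5.2 gives conflicting results for a recorded fever with a blank attribution, and under one of them a child whose only persisting symptom is that fever loses OCR 5

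*SAP*

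**What the plan says.** The endpoint definition is in Protocol 3.2.1 (Table 1, footnote 2) and is repeated in SAP 3.3. A temperature of 38.3°C or more counts against resolution of symptoms "unless attributed to a new process that is unrelated to the prior diagnosis of pneumonia". SAP 3.3 adds a rule that begins "If a subject has a fever according to the measurement taken as a part of vital signs" and ends with the child being analyzed as febrile at that visit.

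SAP 6.5.2 turns this into a derivation from two form items: ACRTEMP (fever recorded in the past 24 hours) and ACRFEV (if yes, was it attributed to an unrelated process). Three statements in that section bear on ACRTEMP=Yes with ACRFEV blank:

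- Lead text: "Fever at the OAV is never missing if the OAV did occur (specifically, ACRTEMP not missing".
- First bullet: if "fever is not indicated as unrelated to prior diagnoses of pneumonia (ACRFEV), then fever at the OAV is present".
- Third bullet: if "relatedness to prior diagnoses of pneumonia (ACRFEV) is missing, then fever at the OAV is missing".

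SAP 6.5.3 then makes a child unresolved if any one symptom is present, "regardless of whether some components of the resolution of symptoms are missing". If no symptom is present and at least one is unknown, "Otherwise, resolution of symptoms is missing at the Outcome Assessment Visit".

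**The concern.** One data pattern gets two answers within one section, so two programmers could derive the primary endpoint differently and each cite the SAP. The endpoint definition treats attribution to another cause as an exception that someone has to make, and a blank field does not make it. The plan uses a similar default elsewhere: Protocol 11.4.1 and SAP 3.3 count a fever that was not re-measured as a fever.

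If the third bullet is coded, the recorded fever is lost for some children. Their DOOR becomes missing, they drop out of the complete-case and according-to-protocol analyses, and the primary analysis replaces their outcome with a draw from a model that cannot see the fever. Section 6.5.2 serves both visits, so the secondary DOOR at Outcome Assessment Visit #2 is affected in the same way.

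**Working it through.** The plan states no figure on this point, so the check is a trace through the rules followed by an illustrative sizing.

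**1. Trace for ACRTEMP=Yes, ACRFEV blank (SAP 6.5.2, 6.5.3, 6.5.5)**

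| Clinical response | Fast breathing or grade 2-3 cough | OCR, third bullet | OCR, lead text or first bullet |
|---|---|---|---|
| Adequate | Either or both | 5 | 5 |
| Adequate | Neither | Missing | 5 |
| Inadequate, no hospitalization | Any | 6 | 6 |
| Inadequate, hospitalized | Any | 7 | 7 |

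Only the second row differs. For that child:

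- Missing OCR makes DOOR missing (6.5.7).
- Missing resolution of symptoms is a listed CC-V1 exclusion (6.3), and ATP-V1 is a subset of CC-V1 (6.3.3).
- The imputation model (8.4.1) contains site, study treatment, initial antibiotic, age group, treatment setting, the other visit's OCR, and daily cough and worst solicited event. It has no fever, temperature, respiratory-rate or visit-day cough term.

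Tables 24 and 25 count only children with complete fever records. A child who keeps OCR 5 through cough or tachypnea would therefore still leave those denominators under the third bullet.

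**2. How many children**

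The documents give neither rate. Assume 2% to 6% of 360 children have ACRTEMP=Yes and 5% to 10% of those lack ACRFEV:

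- Low: 360 × 0.02 × 0.05 = 0.36
- High: 360 × 0.06 × 0.10 = 2.16

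This overstates the count on those rates, because it includes children in the unaffected rows.

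**3. Effect per child on the primary probability P**

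Assume 180 per arm, the same OCR distribution in both arms, 0 antibiotic days on short course and 5 on standard course, and imputation predictors that carry no information beyond arm. P is the average, over short-course children, of the share of standard-course children each one beats.

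- Short-course child: change ≈ (P − w)/180, where w is the share of standard-course children that a short-course OCR 5 child beats.
- Standard-course child: change ≈ (P − b)/180, where b is the share of short-course children who beat a standard-course OCR 5 child.

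| Assumed % in OCR 1/2/3/4/5/6 | P | w | Short-course change | b | Standard-course change |
|---|---|---|---|---|---|
| 55/28/6/2/8/1 | 0.695 | (14+2)/180 = 0.089 | +0.0034 | 178/180 = 0.989 | −0.0016 |
| 40/30/10/5/12/3 | 0.639 | (22+5)/180 = 0.150 | +0.0027 | 175/180 = 0.972 | −0.0019 |
| 75/12/3/1/8/1 | 0.792 | (14+2)/180 = 0.089 | +0.0039 | 178/180 = 0.989 | −0.0011 |

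A simulation that redraws the child's rank from a normal distribution with the arm's mean and standard deviation gives +0.0035, +0.0026 and +0.0041 for short course, and −0.0017, −0.0020 and −0.0012 for standard course. Two affected children give +0.0055 to +0.0082 if both are on short course, or −0.0024 to −0.0037 if both are on standard course. The sample size rests on a departure of 0.60 − 0.50 = 0.10.

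These shifts are illustrations, not bounds. A child with fever alone may have a benign diary, and the actual model would then draw a better rank than the arm mean. The ceiling for one child is 1/180 = 0.0056.

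**The case against.** The best defense is that the third bullet is deliberate. It names the blank case explicitly, and the three ACRTEMP=Yes bullets read naturally as ACRFEV = No, Yes and missing. The lead sentence goes on to call the vital-signs and parent-recorded temperatures supplementary, so its likely purpose is to say that gaps in those fields do not make fever missing. Protocol 11.4 leaves to the SAP what counts as sufficient data for DOOR. SAP 6.5.1 also handles a parallel item in the same way: a non-study antibiotic with a blank attribution (MAVABCP) makes adequate clinical response missing, not failed, unless another field shows failure. Finally, a blank may hide a fever that truly was unrelated, in which case the child belongs in OCR 1 to 4.

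Much of this stands. A missing rule is a legitimate option, and the documents do not force the other one. The conflict remains, though: 6.5.1 never claims its result cannot be missing, whereas 6.5.2 does, and the first bullet literally covers the blank. Some text has to change whichever rule is kept.

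A reader might infer four stronger things that the documents do not support:

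- That every child with a recorded fever and blank attribution loses OCR 5. The trace shows this happens only when fever is the sole persisting symptom and response was adequate.
- That such a child is imputed as an average child. The draw is conditional on arm, strata, site, the other visit's OCR and diary data.
- That only bad outcomes are removed. Some blanks may be unrelated fevers.
- That the bias runs one way. Its sign on the primary estimate depends on arm, and nothing in a blinded trial suggests that blanks would favor one arm.

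**Conclusion.** The contradiction in SAP 6.5.2 is certain from the text. Its consequence under the third bullet is also certain, but narrow: a child with adequate response, normal respiratory rate, cough below grade 2, a recorded fever and a blank attribution has DOOR missing instead of OCR 5, and the fever does not inform the imputed value.

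The effect is minor. On the assumed rates, two or so children per visit is a generous count, and site queries for missing data (Protocol 13) should reduce it. At that count the primary probability moves by less than 0.01 in the illustrations, against a design difference of 0.10. Both the rates and the OCR distributions are assumptions; the documents supply neither. This is a definition to settle before unblinding. It is not a threat to the trial's conclusion.

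**What to change.** Before unblinding:

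1. Replace the third bullet of SAP 6.5.2 with: if ACRTEMP=Yes and ACRFEV is missing, fever at the visit is present. This agrees with the endpoint definition in Protocol 3.2.1 and SAP 3.3, with the first bullet and with the lead text.
2. Align 6.5.2 with the SAP 3.3 rule that a fever measured at the visit counts as fever. At present 6.5.2 treats that measurement as supplementary. State whether the unrelated-cause exception applies to it.
3. Report the number of blank ACRFEV values by arm and visit, and add one sensitivity analysis that treats those fevers as missing.

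The cost is one line in the SAP and one in the code for the first item, a short clarification for the second, and one extra run for the third. The downside is small. A few unrelated fevers with no attribution entered will count as persistent symptoms, and the rule will differ from the one for MAVABCP in 6.5.1; the sensitivity analysis covers both.

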- Subjects will be provided with a memory aid and other study-related materials to record daily temperature, solicited events, concomitant medications, presence of cough, and daily dose administration. Parents will be instructed that any temperatures over 100.9°F should be repeated 15 minutes later in the same manner as the initial temperature. Study staff will instruct the parent/guardian to complete the memory aid in order to document adherence and to bring the medication bottle with them to the Outcome Assessment Visit #1. Study staff will also review the memory aid used to assess specific, solicited events;
- Collection of a throat swab specimen if contributing future use samples;
- Dispense containers for collection of a stool specimen, if participating in future use portion of the study.

Since the Enrollment Visit will occur during Day 3-5 of treatment (Day -3 to -1), the subject will be instructed to complete the originally prescribed medication through Day -1 (after receipt of the last dose of the originally prescribed medication on the fifth consecutive calendar day of treatment) and to start study product on Day 1.

Parents will be educated at the time of their child's enrollment in the study about prompt and adequate treatment for recurrence of symptoms or solicited events. The subject's parent/guardian will be instructed to contact their primary care provider as soon as possible in the event of worsening respiratory status, recurrence of fever, or for other concerns. Parents/guardians will also be asked to contact study personnel in the event of clinical deterioration (i.e., medical visit or hospitalization for pneumonia) or for any severe solicited events.

Study personnel will be available at each site for urgent issues related to the study or for communication with primary care providers who may have questions about the study.

Subjects who do not meet eligibility criteria or decline consent will be instructed to continue their initially prescribed antibiotic unless otherwise advised by their treating clinician.

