11.4.1 Primary Analysis

For the primary analyses, the DOORs will be compared between the 5- and 10-day arms. The sum of the probability that a randomly selected subject will have a better DOOR if assigned to the 5-day arm for Outcome Assessment Visit #1 plus one-half the probability of equal DOORs for Outcome Assessment Visit #1 will be estimated. The null hypothesis to be tested is that the probability is equal to 0.50 (lack of superiority of short-course therapy). The primary analysis will be carried out using the ITT cohort, with missing DOOR values (treated as continuous)

imputed using multiple imputation, utilizing linear regression models corresponding to relevant observed data (baseline covariates and observed DOOR components from an early termination visit, if available). The Mann-Whitney U statistic will be combined across the datasets to give the test statistic and Rubin's Rules used to define distribution of the test statistic under the null hypothesis. The test of the null hypothesis will be two-sided with a Type I error of 0.05. A point estimate of the estimand will be computed by dividing combined test statistic by the number of pairwise comparisons and a confidence interval of the estimand will be computed by inverting the described test of the null hypothesis.

Note: Subjects will be asked to confirm fever with repeat testing after approximately 15 minutes; for analysis purposes, subjects lacking a repeat measurement will be considered as having developed fever.

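### The four fever rules in SAP 6.5.2 omit the 15-minute confirmation that defines fever in the primary endpoint, so, read literally, a child with a normal repeat reading can be scored OCR 5

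*SAP*

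**What the plan says.** **The definition.** In Protocol 3.2.1 (Table 1, note 2), symptoms are unresolved if the child has a temperature of at least 38.3 °C that is "confirmed by repeat measurement after at least 15 minutes, in the 24 hours preceding the Outcome Assessment Visit or measured at the Outcome Assessment Visit"; one put down to a new, unrelated process is exempt. Note 2 to Table 1 in SAP 3.3 carries the same confirmation requirement.

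**No repeat taken.** Protocol 11.4.1 says that "subjects lacking a repeat measurement will be considered as having developed fever". SAP 3.3 agrees for a child with one high reading "but no repeat measurement after at least 15 minutes has been performed, the subject will be analyzed as having a fever". SAP 3.3 also counts a high temperature on the visit vital signs as fever.

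**Data collection.** Protocol 7.2 tells parents that "any temperatures over 100.9°F should be repeated 15 minutes later in the same manner as the initial temperature".

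**The derivation.** SAP 6.5.2 builds fever from two items. ACRTEMP asks: "Has the subject had a recorded temperature > 38.3 °C (100.9 °F) in the past 24 hours? (Yes/No". ACRFEV asks, after a Yes, whether the cause was unrelated to the pneumonia. The four rules are:
- ACRTEMP high, not marked unrelated: fever present.
- ACRTEMP high, marked unrelated: fever absent.
- ACRTEMP high, ACRFEV missing: fever missing.
- ACRTEMP below threshold: fever absent.

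Just above these rules, 6.5.2 states the confirmation test, but as the definition of fever observed as a solicited event. None of the four rules uses that term. The same paragraph says of the home readings that "the actual temperatures reported by parents and recorded on the solicited events form (SRS) are treated as optional and supplemental data", and it treats the visit vital signs likewise.

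**The concern.** The definition gives three outcomes for a high home reading: confirmed (fever), not repeated (fever by default) and repeated but normal (not fever). The rules cannot tell the third from the first two, because neither ACRTEMP nor ACRFEV asks about a repeat.

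This reaches the primary endpoint. Under SAP 6.5.3, fever alone is enough for symptoms to be unresolved. Under SAP 6.5.5, unresolved symptoms with adequate clinical response give OCR 5, which ranks below a child whose symptoms resolved but who had a grade 3 solicited event. The same derivation supplies resolution of symptoms and the fever rows of SAP Tables 24-25.

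Two sections of the SAP therefore give different values for the same child, and two programmers could build different primary datasets. The fever analysis in Protocol 11.4.2 and the DSMB display in SAP 6.6 both require confirmation, whereas SAP 8.2.4 refers to 6.5.2 for the final analysis. SAP 13 nevertheless declares no change from the protocol's planned analyses.

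**Working it through.** **Step 1: the plan's own figure.** The point rests on no figure in the plan. For context, SAP 5 uses Noether's formula: N = (1.960 + 1.282)² / [12 × 0.5 × 0.5 × (0.60 − 0.50)²] = 350.2, against the stated 360 (power at 360: 90.8%). Then 360 / 0.90 = 400. Fever does not enter this calculation.

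**Step 2: the two texts side by side.** Temperatures are in °C. ACRTEMP is answered as worded, and ACRFEV is handled identically in both columns, so the only difference is confirmation.

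| Home reading, then repeat | ACRFEV | SAP 3.3 | SAP 6.5.2 rules |
|---|---|---|---|
| 38.8, then 37.2 | No | absent | **present** |
| 38.8, then 37.2 | Yes | absent | absent |
| 38.8, then 37.2 | missing | absent | **missing** |
| 38.8, then 38.6 | No / Yes / missing | present / absent / missing | same |
| 38.8, no repeat | No / Yes / missing | present / absent / missing | same |
| 37.5, no repeat | any | absent | absent |

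The texts differ only when the repeat was normal and ACRFEV is No or missing.

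**Step 3: through to OCR.** In the first row, a child with adequate clinical response, normal respiratory rate and cough below grade 2 is OCR 1-4 under SAP 3.3 and OCR 5 under 6.5.2. A child with raised respiratory rate or grade 2-3 cough is OCR 5 either way, and one without adequate response is OCR 6 or worse either way. In the third row, if respiratory rate and cough are normal, resolution of symptoms and hence OCR become missing and must be imputed.

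**Step 4: threshold.** The ACRTEMP question uses >38.3 °C and the rules use ≥38.3 °C. They disagree only for a reading of exactly 38.3 °C.

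**Step 5: size, on assumed inputs.** Suppose OCR shares of 45/25/12/3/12/2/1/0% in both arms, with 0 against 5 antibiotic days, so that every OCR tie goes to short course. Then Pr(higher DOOR) = (1 + Σp²)/2 = (1 + 0.2952)/2 = 0.648. Now move a fraction q of OCR 1-4 (85% of children) to OCR 5:

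| q | Moved, of 400 | Both arms equally | Short course only |
|---|---|---|---|
| 0.5% | 1.7 | 0.647 | 0.645 |
| 1% | 3.4 | 0.646 | 0.643 |
| 2% | 6.8 | 0.644 | 0.638 |
| 5% | 17.0 | 0.640 | 0.623 |

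The equal-arms estimate falls because fewer pairs tie on OCR and so fewer go to short course on antibiotic days.

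An upper illustration of the count: if 2-6% of children have a high first reading, every family repeats it and 20-40% of repeats are normal, then 360 × 0.02 × 0.20 = 1.4 to 360 × 0.06 × 0.40 = 8.6 children are affected. The fever rate is then inflated by 1/(1 − 0.20) = 1.25 to 1/(1 − 0.40) = 1.67. If half of families repeat, these become 0.7 to 4.3 children and 1.11 to 1.25. The other conditions in Step 3 lower the number reaching OCR 5 further.

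**The case against.** The strongest reply is that ACRTEMP is known only from its question text. Staff complete it at a visit where they also review the memory aid, and the manual of procedures or CRF instructions, which are not among the documents, may tell them to answer No after a normal repeat. A reader might infer from the rules that children will certainly be misclassified. The documents do not support that; they show only what the rules do when the item is answered as worded. Such an instruction would soften the problem in practice, but the SAP would still need to state it, because the derivation is meant to be reproducible from the SAP.

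A second reply is that 6.5.2 does contain the confirmation test and calls the home readings supplemental in deciding on fever. It would indeed be wrong to say that the section ignores confirmation. But the test is attached to a term no rule uses, and no rule says how supplemental data change the result.

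A third reply is that the effect is small. Outcomes are assessed blind, families who take no repeat are scored the same under both texts, and several conditions must hold before a child moves to OCR 5. This stands.

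**Conclusion.** The point holds for the four rules as written: they do not implement the endpoint definition in Protocol 3.2.1 and SAP 3.3. The direct error is a normal repeat scored as fever when ACRFEV is No. A secondary one is fever set to missing when ACRFEV is missing.

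The size is unknown, because the documents give no rate of unconfirmed fever. Given blinding, the number is probably small and similar in both arms, with a minor effect on Pr(higher DOOR): in the illustration, 0.008 or less for up to 5% affected equally. That rests on the assumed OCR shares and on ACRTEMP being answered literally. The planned sample size is unaffected.

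Two stronger inferences should not be drawn. One is that the primary conclusion is at risk; nothing in the documents shows that. The other is that the noise necessarily pulls the OCR non-inferiority estimate towards 0.5. If a fraction q moves to OCR 5 in each arm, the net contrast among pairs within OCR 1-4 shrinks by (1 − q)² and that between OCR 1-4 and OCR 5 by (1 − q), while contrasts with OCR 6-8 are unchanged. The net direction therefore depends on whether these components point the same way.

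The change is worth making because it concerns the primary endpoint's derivation and is cheap.

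**What to change.** Rewrite the SAP 6.5.2 rules in this order:

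(a) A temperature of at least 38.3 °C on the visit vital signs counts as fever, as in SAP 3.3. This must come first: a rule that simply set fever to absent after a normal home repeat would score as afebrile a child who is febrile at the visit.

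(b) Otherwise, any home reading of at least 38.3 °C counts as fever if the repeat was also at least 38.3 °C or no repeat was recorded. It does not count if the recorded repeat was below 38.3 °C. The solicited-event term already defined in 6.5.2, with its window of the visit day and the day before, can serve here.

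(c) If the home temperatures on the solicited events form are unavailable, use ACRTEMP.

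(d) ACRFEV then applies as now. Because it is asked only after ACRTEMP is Yes, the text should say what happens when (a) or (b) finds fever and ACRFEV was not asked.

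Align the ACRTEMP wording to ≥38.3 °C, and remove the statement in 6.5.2 that fever is never missing when the visit took place, which its third rule contradicts. If CRF instructions already require a No after a normal repeat, cite them.

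The cost is SAP wording and a few lines of code. Section 6.5.2 already treats first and confirmatory home readings as recorded data.
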